FP interventions have primarily focused on patient-provider communication and increasing knowledge²¹⁻ ²³, but in a recent study, half of 13-21-year old males who were told they were at risk for infertility still declined FP before treatment²⁴. Notably, *parents' recommendation to bank* was one of the strongest predictors of FP^{25,26}. However, research has shown that parents do not prioritize fertility in the setting of their child's new cancer diagnosis^{27,28}. AYA survivors and parents in our recent pilot study had discordant attitudes about FP, with parents significantly underestimating the impact of potential infertility on their sons. Thus, knowledge is critical, but other *individual and family* factors must be identified to explain gaps between those pursue and decline FP. The relative ease but underutilization of sperm banking, as well as the psychosocial implications of infertility, demonstrate a need for novel family-centered interventions at the time of diagnosis to optimize FP uptake and decision quality for this unique and vulnerable population^{25,26}. Such interventions have improved parent-child communication about sexual health topics and have shown promise in other conditions such as multiple sclerosis. However, research at the time of diagnosis has been limited by concerns that the burden of participating could be too heavy at such a tumultuous time. Previous research has shown that participating in FP focused research at the time of diagnosis is rated as beneficial or neutral by AYAs and families²⁹. In our ongoing observational pilot (IRB17-00883) our recruitment rate is 93% for Visit 1 and 81% for Visit 2, which shows that a study of this kind is feasible at the time of diagnosis.

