- 3. *Many parents poorly estimate their sons/daughters' reproductive desires and worries, and struggle with separating their own desires from those of their children⁵².* A 2012 study in adolescent females recently diagnosed with cancer showed parents underestimated their daughters' reproductive concerns²⁸. Similarly, AYA males recently diagnosed with cancer ranked fertility in the top three life priorities, whereas parents were more concerned with their sons' health²⁷. Further, while many parents want to be grandparents in the future, they are often more willing to consider alternate means of family building (e.g. adoption) than their sons⁵³. Discordance, and/or parents' lack of awareness of their sons' reproductive goals and concerns, may ultimately lead to lower decision quality.
- 4. Notably, a recent study among 13-21-year old males within one week of initiation of cancer treatment demonstrated parents' recommendation to bank sperm, as compared with the medical

team, was the most robust predictor of a FP attempt^{26,49}. Thus, an intervention designed to increase caregiver-child communication should be examined within an established health behavior framework to examine its preliminary efficiency at increasing rates of FP in AYAs.

We completed an observational pilot study (IRB17-00883) testing feasibility and initial effects of a decision tool examining individual and family factors that impact FP decisions. The pilot informed the development of the decision tool that will be used in this study intervention, as well as the interviews used at the 1-month and 1-year follow-up. Recruitment rates were above 90% for visit 1, further demonstrating the feasibility of this type of study at the time of diagnosis.

4.0 **Study Endpoints**

The overarching goal of this project is to examine preliminary efficacy of the psychoeducational intervention in a pilot RCT. The *primary endpoint* is FP uptake following the intervention. The *secondary endpoints* are the Brief Subjective Decision Quality (BSDQ) questionnaire scores at 1-month and 1-year post-intervention and the change in Parent Adolescent Communication Scale (PACS) scores from baseline to 1-month and 1-year post-intervention.

5.0 **Study Intervention**

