- 4. All study personnel who will be working with data or protected health information will be properly trained, which includes completing the online Collaborative Institutional Training Initiative (CITI) certification and undergoing a day-long instructional seminar at the hospital for protecting human subjects and engaging in best practices for responsible conduct of research. Additionally, per NIH policy, clinical trial staff who are involved in the design, conduct, oversight, or management of the trial will be trained in Good Clinical Practice (GCP).

- 5. Staff will receive extensive training in administration of all questionnaires as well as professional behavior with families. The interventionist will have additional training in ENRICH/ECHO, an oncofertility communication training program.
- 6. Staff will be trained to contact the PI immediately if an adverse event occurs, and corrective action, including IRB notification, will occur, if necessary.
- 7. Once enrolled in the study, participants (patients and parent(s)) will receive a study ID number. This number will be entered on their survey, be it paper or online (i.e., using REDCap, an online survey system that is housed securely on the NCH research drive). The only link between the participant's name and study ID will be an electronic tracking sheet, which will be password protected and stored on the secured research network drive of the hospital. The tracking sheet will contain the following protected health information: name, medical record number, date of birth, address, phone number, email address, diagnosis, and dates of study visits. Only direct study personnel will have access to this file. Participants will be identified in all datasets by their study ID.
- 8. If participants find any of the questions upsetting, the study team will be available to discuss the concerns or reconnect the participant to their assigned psychosocial provider at Nationwide Children's Hospital. Participants may also skip any questions that they do not want to answer.
- 9. Online questionnaire data and voice recordings will be housed behind a secure firewall on the NCH research internet server. Any data that is not collected in a digital format will be kept in a locked cabinet within a locked office at the hospital. Only study personnel will have access to this information.

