Data Collection Procedures: Data described in Section 6.0 will be collected for all participants. Data will be collected by trained research staff using an online survey tool (e.g., REDCap) or paper and pen questionnaires. Some data may be obtained from the participant's electronic medical record. Data collected at Visit 1 will be collected before the intervention begins, and data collected at Visits 2 and 3 will be collected after the intervention ends.

End of Study Definition: A participant is considered to have completed the study if they completed the baseline assessment, as well as the 1-month and 1-year follow-up assessments.

Lost-to-Follow-up Definition: A participant will be considered lost to follow-up if they fail to return for scheduled visits and study staff are unable to contact the participant after at least 3 attempts via phone or email.

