17.0 Data Management* and Confidentiality

Data Collection & Management: Data collection will be the responsibility of the study staff under the supervision of the PI. The PI will be responsible for ensuring the accuracy, completeness, legibility, and timeliness of the data reported.

All source documents will be completed in a neat, legible manner to ensure accurate interpretation of data. Hardcopies of the study visit worksheets will be provided for use as source document worksheets for recording data for each participant consented/enrolled in the study. Data recorded in the electronic case report form (eCRF) derived from source documents will be consistent with the data recorded on the source documents.

Clinical data (including AEs) and clinical laboratory data will be entered into secure study databases, if needed. The data system includes password protection and internal quality checks, such as automatic range checks, to identify data that appear inconsistent, incomplete, or inaccurate. Clinical data will be entered directly from the source documents.

Only authorized study staff will have access to study data.

Sample Size Determination: The sample was determined based on the medium-large effects found in our previous work and work by Klosky et al. and is sufficient to find similar sized effects; thus our proposed sample size will enable us to detect effect sizes previously found in the literature^{26,54-56}.

A sample size of n=20 per group will provide 80% power to detect large effect sizes of w=.45 for the chisquare analysis and d=.91 for the independent samples t-test. Because this is a pilot study, the focus will be on generating reliable effect size estimates for our primary outcome (FP uptake) comparing the intervention to standard care, rather than on statistical significance (using two-sided type I error rates (alpha values) of no more than .05). The proposed sample size is sufficient for gleaning this information.

Data Analysis Plan: Analyses will be conducted according to intent-to-treat methods, in which all randomized participants are included. Summary statistics will be calculated and qualitative methods used to evaluate the feasibility of recruiting and enrolling children.

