Chi-squared and t-tests will be used to evaluate primary and secondary outcomes. A chi-square analyses will examine the primary outcome of FP uptake (Y/N) as a function of treatment group status An independent samples t-test will examine whether the secondary outcomes of decision quality (numerical score on the BSDQ and family communication (numerical score on the PACS and difference scores on the PACS for AYA and parents) change between 1-month and 1-year follow-ups. Pearson's r correlations will be run to see if FP uptake (Y/N) is related to decision quality or family communication.

The two groups (intervention and control) will be examined in an *exploratory* manner to assess potential differences in factors known to affect FP decisions such as demographics (e.g. age), urgency to start treatment, knowledge, provider recommendation, and parent recommendation, as well as novel factors such as quality of parent-child communication. We will also examine these baseline factors as covariates within an analysis of covariance to see if might have a substantial impact on our effect size estimates for the larger RCT.

Quality Control of Data: Internal quality management of study conduct, data collection, documentation and completion will be conducted, under the direction of the PI. Quality control (QC) procedures will be implemented as follows:

- Informed consent: Study staff will review both the documentation of the consenting process as well as a percentage of the completed consent documents. This review will evaluate compliance with GCP, accuracy, and completeness. Feedback will be provided to the study team to ensure proper consenting procedures are followed.
- Source documents and the electronic data: Some data will be initially captured on source documents and will ultimately be entered into the study database. Some data will be entered directly into an electronic data capture system. To ensure accuracy of data initially captured on source documents, site staff will compare a representative sample of source data against the database, targeting key data points in that review. Some data will be entered directly into study databases. Electronic databases will be programed to alter study staff and/or participants of out of range values and/or potential errors.

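### The 1-year BSDQ comparison is labelled intent-to-treat, but its t-test can use only participants who have a score, and no missing-data method is given

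*Combined protocol and SAP*

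**What the plan says.** The Data Analysis Plan in Section 17.0 opens with the promise "Analyses will be conducted according to intent-to-treat methods, in which all randomized participants are included". It then names the tests: "Chi-squared and t-tests will be used to evaluate primary and secondary outcomes". For the secondary scores it adds: "An independent samples t-test will examine whether the secondary outcomes of decision quality" and family communication change between the two follow-ups. Read with the hypotheses in Section 2.0, I take this to mean a comparison of arms at each visit.

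Section 4.0 makes two sets of scores secondary endpoints. Decision quality is represented by "Brief Subjective Decision Quality (BSDQ) questionnaire scores at 1-month and 1-year post-intervention". For family communication, Section 4.0 specifies a "change in Parent Adolescent Communication Scale (PACS) scores from baseline to 1-month and 1-year post-intervention".

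The protocol foresees missing scores. Section 6.0 defines loss to follow-up ("A participant will be considered lost to follow-up if they fail to return for scheduled visits" and at least three contact attempts fail). It also allows item non-response: "Participants may also skip any questions that they do not want to answer". Section 14.0 encourages data collection after withdrawal from the intervention. None of these says how a randomised participant without a score enters the analysis. The protocol names no imputation, likelihood-based model, missing-data assumption or sensitivity analysis. The exploratory analysis of covariance in Section 17.0 does not fill the gap, since as described it too needs an observed outcome.

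On retention, Section 13.0 reports 100% engagement at 1 month in previous work and expects similarly high retention here. It lists measures to keep families engaged through 1 year but gives no 1-year figure.

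**The concern.** A two-sample t-test at a visit uses only the scores recorded at that visit. Wherever one is missing, the promise to include everyone randomised is not met, and the result is an available-case comparison. If the participants who do not return at 1 year differ in decision quality from those who do, and the pattern differs between arms, the estimated difference is shifted.

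The t-test also discards usable information. BSDQ is collected at both follow-ups, so someone seen at 1 month but not at 1 year has a score that helps predict the missing one.

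At stake is the 1-year estimate of decision quality and how it is described. Section 17.0 puts effect-size estimation ahead of significance and looks ahead to a larger trial, so a shifted estimate under an intent-to-treat label could be carried forward.

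**Working it through.** **Inputs from the protocol.** 20 per arm, 1:1 allocation, two-sided alpha .05, d=.91 for the t-test and w=.45 for the chi-square at 80% power (Sections 6.0 and 17.0). BSDQ is measured at 1 month and 1 year.

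**Inputs assumed.** 1-year base loss 15-30%, true difference .5 SD, correlation .6 between visits. The protocol gives none of these.

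**Step 1: the plan's own power.** Noncentral t with 38 degrees of freedom and noncentrality .91 × √(20×20/40) = 2.88 gives 80.1%. Noncentral chi-square with 1 degree of freedom and noncentrality 40 × .45² = 8.1 gives 81.2%. Both reproduce the stated 80%, with all 20 per arm scored.

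**Step 2: loss of scores.** Power at d=.91 falls as follows:

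| Loss | Scored per arm | Power |
|---|---|---|
| 0% | 20 | 80.1% |
| 10% | 18 | 75.6% |
| 20% | 16 | 70.2% |
| 30% | 14 | 64.0% |

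The standard error of the difference is √(2/n) SD. With 16 per arm it is √(2/16) = .35 SD.

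**Step 3: how bias arises.** In one arm, the mean of returners differs from the full mean by (share missing) × (mean gap between returners and non-returners). The bias in the arm difference is the difference between the two arms' products.

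- 30% missing in one arm with a .5 SD gap and no selection in the other: .30 × .5 = .15 SD.
- The same .5 SD gap in both arms, 30% v 15% missing: (.30 - .15) × .5 = .075 SD.
- Equal shares and equal gaps: zero.

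**Step 4: loss that depends on the 1-month score.** The model is logit P(missing at 1 year) = logit(base loss) - slope × 1-month score. Scores have SD 1; the control mean is 0 and the intervention mean is .5 at both visits. The slope is .5 to 1.0, with 20,000 simulated trials per scenario.

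| Which arm selects | Base loss | Bias of available-case difference (SD) |
|---|---|---|
| Both, same slope | 20% in each | -.01 (slope .5) to -.035 (slope 1.0) |
| Both, same slope | 30% control, 15% intervention | -.05 to -.10 |
| Control only | 20% | -.12 (slope 1.0) |
| Control only | 30% | -.17 (slope 1.0) |
| Intervention only | 20% | +.09 (slope 1.0) |

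The first row is not zero because the arms' 1-month means differ, so the same rule removes more of the control arm. More base loss moves each one-arm figure further from zero.

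A maximum-likelihood estimate using both visits has bias within .01 SD in these scenarios and a slightly smaller standard error (about .35 v .36).

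**Step 5: size against noise.** .10/.35 = .29 and .17/.35 = .49, so the largest of these biases is about half a standard error.

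**Step 6: loss that depends on the unseen 1-year score.** The available-case bias was -.16 and -.21 SD in two such scenarios, and the likelihood estimate still had -.10 and -.14. As .10/.16 = .63 and .14/.21 = .67, about two-thirds of the bias remains and a third is removed.

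**The case against.** The strongest reply is that this is a pilot whose stated focus is the effect size for FP uptake, and that the likely bias in a secondary score is well inside the sampling error. Relabelling the t-tests as available-case and reporting missing counts would cure the misdescription with no new model. The model's advantage is also greatest under the loss mechanism it assumes. Even there the gain is modest: with 30% v 15% base loss and slope 1.0, root mean squared error is .369 SD for the available-case difference and .350 for the likelihood estimate. A participant missing both follow-ups contributes to neither, so the model does not literally include everyone randomised either.

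Most of that stands, and it limits how strongly the point can be put. It does not remove the mismatch between the stated population and the stated test. Nor does it justify discarding 1-month scores that are already being collected.

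A reader might infer more than the documents support:

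- **That including everyone is impossible for BSDQ and PACS at any visit.** Section 13.0 expects 100% engagement at 1 month. If that is met and the questionnaires are completed, the promise holds there.
- **That the pilot shows 19% loss by Visit 2.** Section 2.0 says "our recruitment rate is 93% for Visit 1 and 81% for Visit 2". It calls this a recruitment rate, in a pilot described there as ongoing, so it should not be cited as retention.
- **That 1-year PACS suffers the same attrition bias.** The Visit 3 activities in Section 6.0 do not list PACS at all, although Section 4.0 makes it an endpoint. That is a separate gap.
- **That the secondary results will be biased.** Bias needs loss related to outcome in a way that differs between arms.

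**Conclusion.** The point holds for the 1-year BSDQ comparison. As written, it is an available-case t-test presented as an intent-to-treat analysis of everyone randomised, with no missing-data method. The promise may fail, mainly at 1 year, where no retention figure is given.

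Under the assumptions above, the bias is about -.01 to -.10 SD when both arms select alike. When one arm selects, it is about +.09 SD (intervention arm, 20% base loss) to -.17 SD (control arm, 30% base loss). This is small against a standard error of about .35 SD, though .17 SD would be about a third of a true .5 SD difference (.17/.5 = .34). All these sizes rest on assumed loss rates, slopes and correlation. With full 1-year return the bias would be nil. The analysis of FP uptake is not affected by this point.

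**What to change.** For BSDQ, replace the visit-wise t-tests by a likelihood-based repeated-measures model, fitted separately for each informant. Include arm, visit and arm-by-visit, with unstructured covariance and small-sample degrees of freedom, and report the arm difference at each visit. Two visits need only three covariance parameters, which is workable at this size.

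Describe the analysis set as all randomised participants with at least one follow-up score. Report missing counts by arm and visit, and keep the all-randomised description for FP uptake.

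Add a simple sensitivity analysis that shifts the missing 1-year scores. Each arm's mean moves by (share missing) × (shift): with 20% missing in one arm and a shift of -.5 SD, .20 × -.5 = -.10 SD.

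Before pooling visits, reconcile Section 6.0, which describes BSDQ as six items at Visit 2 and seven at Visit 3.

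The cost is a change of analysis-plan wording and a standard model, with no new visits or data. The downside is the assumption that loss is explained by observed scores. Where loss depends on the unseen 1-year score, the model removes only about a third of the bias, which is why the sensitivity analysis is needed.

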Aims: This randomized clinical trial (RCT) will test the feasibility, acceptability, and preliminary efficacy of a novel family-centered, psychoeducational intervention with known and newly identified factors to improve fertility preservation (FP) uptake, decision quality, and family communication among male adolescents and young adults (AYAs) newly diagnosed with cancer. The primary aim of this project is to examine preliminary efficacy of the psychoeducational intervention with regard to FP uptake.

Hypotheses: The primary hypothesis is that compared to standard of care control group (routine fertility consult at diagnosis, n=20), AYAs in the intervention arm (routine fertility consult at diagnosis + FP Decision Tool and Facilitated Conversation by trained interventionist; n=20) will have higher rates of FP uptake. The secondary hypotheses are that families in the intervention group will report better FP decision quality and report improvements in family communication, compared to those in the control arm.

Rationale: Nearly 9,000 males under age 20 are diagnosed with cancer in the U.S. each year¹. With 5-year survival rates exceeding 80%, the population of male childhood cancer survivors is now close to 200,000². Unfortunately, approximately 50% of male survivors have impaired fertility³⁻⁵, which can impede psychosexual development and diminish quality of life (QoL)⁶. Sperm banking is an established and effective method of FP for pubertal males⁷, yet only 25% of eligible adolescents bank sperm prior to

treatment⁸⁻¹². As these AYAs complete therapy and approach their reproductive years, many survivors and their parents *regret* missed opportunities for FP and report *distress* about potential infertility¹³⁻¹⁶.

Significant knowledge gaps exist with regard to pediatric FP:

- 1. Most research examining FP decisions has focused on females^{17,18}, despite a higher prevalence of cancer and treatment-related infertility in males¹⁹;
- 2. Many studies examining FP predictors have been conducted years after therapy and are subject to recall bias^{15,20};
- 3. Little attention has been paid to *decision quality* (satisfaction/regret) soon after FP decisions are made;
- 4. Although parents make most healthcare decisions even in late adolescence/young adulthood, *family factors* including parent-child communication about FP, have not been examined.

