- *Informed Consent:* Informed consent (and assent for participants 12-17 years of age) is obtained by study staff before data collection procedures or randomization. For adolescents between 12-17 years of age, informed consent will be obtained by a parent or legal guardian, and assent will be provided by the adolescent. Those who are between 18-25-years of age will provide informed consent for themselves to participate.
- *Demographics:* Research staff ask participants to answer questions about age, race, ethnicity, religion, education, income, whom they live with, and their relationship to their child. AYAs will be asked to answer an additional four questions about their communiation with their parents. These questions were taken from the Parent-Adolescent Communication Scale (PACS).
- *Randomization:* Families who consent to participate will be randomized (by the interventionist) to the control arm or intervention arm (family-centered psychoeducational intervention) after completing baseline measures. If the family is randomized to the control arm, the interventionist will inform the family that they were randomized to the control group and debrief the family. If the family is randomized to the intervention arm, the interventionist will inform the family that they are conduct the interventionist will inform the family that randomized to the treatment group and conduct the intervention immediately following randomization.

1-month Follow-up (Visit 2, Baseline + 1 to 2 months): At the 1-month follow-up (Visit 2) research staff will contact control and intervention families in-person (at inpatient or outpatient clinic) or via phone or email. Families (AYAs and parents) will be reminded about the study and be asked to complete follow-up activities. All measures will be completed by the child and both caregivers (when available). If the child and/or second caregiver did not complete Visit 1, they will be invited to complete Visit 2. The activities completed at Visit 2 include:

- *FP Decision Survey:* Participants will complete a brief survey about their FP decision. Items will include questions such as who participants talked to about their FP decision and who made the final decision regarding FP. Surveys will not be scored but questions will be used to guide analyses.

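### The stated test of decision quality and family communication looks at change from 1 month to 1 year and names no arm, and the listed visits cannot supply the PACS change-from-baseline endpoint

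*Combined protocol and SAP*

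**What the plan says.** **Hypotheses and endpoints.** Section 2.0 states that "families in the intervention group will report better FP decision quality and report improvements in family communication, compared to those in the control arm". Section 4.0 sets the secondary endpoints as the Brief Subjective Decision Quality (BSDQ) score at 1 month and at 1 year, and "the change in Parent Adolescent Communication Scale (PACS) scores from baseline to 1-month and 1-year post-intervention".

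**Analysis.** In the Data Analysis Plan of Section 17.0, the chi-square test "will examine the primary outcome of FP uptake (Y/N) as a function of treatment group status". The next sentence covers the secondary outcomes: "An independent samples t-test will examine whether the secondary outcomes of decision quality" and family communication "change between 1-month and 1-year follow-ups". It does not mention treatment group. Under family communication it counts PACS scores and also difference scores for the adolescents and young adults (AYAs) and parents, without saying what is subtracted from what.

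**Sizing.** Section 17.0 gives 80% power for the independent-samples t-test at d=.91 with 20 per group. It places the pilot's focus on "generating reliable effect size estimates for our primary outcome (FP uptake) comparing the intervention to standard care".

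**Visits (Section 6.0).**

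| Visit | PACS listed | BSDQ listed |
|---|---|---|
| 1 (baseline) | Four items, AYAs only ("AYAs will be asked to answer an additional four questions") | None |
| 2 (1 month) | 20 items, AYAs and both parents | Six items, scored 0-7 |
| 3 (1 year) | None | Seven items, scored 0-7 |

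The data list under Handling of Data in Section 17.0 mentions the PACS survey but gives no timing.

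**The concern.** The hypotheses ask whether the arms differ. The test sentence asks whether scores move between two follow-up visits. The sentence just before it names the arm, so the omission is not simply house style. An analyst who follows the sentence would not estimate either Section 4.0 endpoint. Leaving the contrast open would also let its meaning be settled after the data are seen.

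The PACS problem is separate and does not depend on how the test sentence is read. Section 4.0 needs PACS at baseline, 1 month and 1 year, and the visit lists do not provide this.

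At stake are the trial's estimates for decision quality and family communication. The primary analysis of fertility preservation (FP) uptake is explicitly by arm and is not touched.

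**Working it through.** **1. The plan's own figure.** Inputs from Section 17.0: n=20 per arm, d=.91, two-sided alpha .05. The noncentrality is d × √(n/2) = 0.91 × √10 = 2.88, on 38 degrees of freedom. Power is 0.801, and the smallest d with 80% power is 0.909. The stated 80% is reproduced as a comparison of 20 with 20. If 40 scores at one visit were set against 40 at the other as independent, the detectable difference would be 0.63 SD. The sizing therefore describes arms, and the test sentence describes time.

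**2. Three readings of the test sentence.**

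- *Arms compared at each visit.* This matches Sections 2.0 and 4.0 for BSDQ. Only the wording is wrong.
- *All families, 1 month against 1 year.* No arm effect is estimated, and an unpaired test is applied to paired scores. With a sustained 0.91 SD benefit it rejects in about 1.2%, 0.3% and 0.03% of trials at within-person correlation r = 0.3, 0.5 and 0.7.
- *Arms compared on 1-month-to-1-year change.* With an arm effect of d₁ at 1 month and d₂ at 1 year, the contrast estimates d₂ − d₁. Section 6.0 states that "data collected at Visits 2 and 3 will be collected after the intervention ends", so neither visit is a pre-intervention reference. If d₂ = d₁, the expected estimate is zero.

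**3. Size under the third reading.** Assumptions, since the documents give no such values: normal scores, 20 per arm, one score per family, r from 0.3 to 0.7, and a benefit that either persists or halves by 1 year. The SD of change is √(2(1 − r)), which is 1.00 at r = 0.5. For d₁ = 0.91 halving, d₂ − d₁ = 0.455 − 0.91 = −0.455 SD.

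| True effect at 1 month (SD) | Power, arms compared at 1 month | Change contrast, effect sustained | Change contrast, effect halved | Halved: significant favouring control, r = 0.3 / 0.5 / 0.7 |
|---|---|---|---|---|
| 0.50 | 34% | about 0.00 | −0.25 | 10% / 12% / 17% |
| 0.65 | 52% | about 0.00 | −0.33 | 13% / 17% / 25% |
| 0.91 | 80% | about 0.00 | −0.46 | 22% / 29% / 44% |

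With a sustained effect, the change contrast rejects in 4.7% to 5.2% of trials in all nine settings, which is the nominal error rate. In the halved case the intervention arm is better at both visits, yet the sign of the contrast favours control.

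**4. PACS, endpoint against visits.**

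- Full-scale change, baseline to 1 month: needs 20 items at both visits, and Visit 1 lists four. Not computable for anyone.
- Parents: no PACS is listed at baseline, so no change score of any kind.
- AYAs: at most a four-item change to 1 month.
- 1 year: no PACS is listed, so neither change to 1 year nor the 1-month-to-1-year contrast in Section 17.0 can be run.

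**5. Precision of an arm comparison at each visit.** The half-width is about t × √(2/n) SD. With 20 per arm: 2.02 × √(2/20) ≈ 0.64. With an assumed 16 per arm left at 1 year: 2.04 × √(2/16) ≈ 0.72.

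**The case against.** The strongest reply is that the intent can be recovered. The t-test is called independent-samples, it is sized for 20 per group, the plan introduces t-tests as the means of evaluating the stated outcomes, and Sections 2.0 and 4.0 define those outcomes and the arm hypotheses. This stands as evidence of intent. A reader might infer that the trial never meant to compare arms on these outcomes, and the documents do not support that. But intent does not repair the sentence. Adding the arm to it gives arms compared on 1-month-to-1-year change, which is neither Section 4.0 endpoint. The rest of the plan does not fill the gap. The Pearson correlations relate scores to FP uptake. The exploratory group comparison concerns factors affecting the decision, which it then calls baseline factors when using them as covariates.

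A second reply is that the figures for an effect favouring control need one particular reading plus an assumed fade and correlation. That is right. They illustrate a hypothetical and do not predict a planned result. The cancellation of a sustained effect needs only that reading.

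A third reply concerns PACS. A reader might infer that nothing from the PACS endpoint can be reported. That goes too far. A four-item AYA change to 1 month may be available. The Visit 3 list is worded as inclusive, and Sections 4.0 and 17.0 both expect a 1-year PACS, so its absence may be an omission from the list. The Visit 1 list is worded as complete, so the baseline gap stands.

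Finally, this is a pilot focused on estimating the effect on FP uptake. That limits the importance of the point, but these remain named secondary endpoints.

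**Conclusion.** The plan is wrong as written, for secondary endpoints only. The test sentence does not match the hypotheses or the endpoints. If it is followed on the change-by-arm reading, a lasting benefit on BSDQ is estimated as about zero. If it is followed as a comparison over time, no arm effect is estimated at all. The harm depends on the sentence being followed literally. If the team compares arms at each visit, as the sizing suggests, only the wording is at fault. The fade and correlation figures rest on the stated assumptions.

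The PACS mismatch holds on the text under any reading: full-scale change from baseline is not computable, parents have no listed baseline, and no 1-year PACS is listed.

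The six-item and seven-item BSDQ descriptions are a minor inconsistency. A reader might infer that the 1-month and 1-year scores are on different scales. Both are given as 0-7, so this may be only a slip in description.

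**What to change.** **BSDQ.** Replace the test sentence with: *BSDQ at 1 month and at 1 year will each be compared between intervention and control (independent-samples t-test, intention to treat), reporting the arm difference and 95% CI at each visit, with AYA and caregiver scores analysed separately.* State how two caregivers in one family are handled, for example by the mean of their scores. Section 12.0 plans 70 caregivers for 40 AYAs, so this will arise often. Reconcile the six-item and seven-item descriptions.

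**PACS.** Reconcile Section 4.0 with the Section 6.0 visit lists.

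- If the lists are right, compare 1-month PACS by arm, adjusted for the four baseline items for AYAs, and amend Section 4.0.
- If a 1-year PACS is intended, as Sections 4.0 and 17.0 suggest, list it at the already scheduled Visit 3 and compare arms there.
- Keep full-scale change from baseline only if the full scale is in fact given at Visit 1.
- State whether the PACS difference scores mean change from baseline or AYA-parent discrepancy. If discrepancy, compare it by arm too.

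**Cost.** For BSDQ, wording only: no new data or participants, and the existing sizing applies if all 40 AYAs are analysed. For PACS, wording only, or a 20-item scale added to an existing visit. If the visit lists are right and PACS is not added at Visit 3, the 1-year and full-scale change-from-baseline PACS endpoints are given up.
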